#### **4.5.5 Treatment Beyond Disease Progression**

As described in [Section 1.1.10](#) accumulating evidence indicates that subjects treated with immunotherapy may derive clinical benefit despite evidence of progressive disease (PD).

Subjects will be permitted to continue with treatment beyond initial RECIST 1.1 defined PD as long as they meet the following criteria:

- Investigator-assessed clinical benefit
- Subject is tolerating study drugs
- Subject has provided written informed consent prior to receiving additional study treatment

The assessment of clinical benefit should take into account whether the subject is clinically deteriorating and unlikely to receive further benefit from continued treatment.

All decisions to continue treatment beyond progression must be discussed with the BMS Medical Monitor and documented in the study records.

Subjects should discontinue study therapy upon evidence of further progression, defined as an additional 10% or greater increase in tumor burden from time of initial progression (including all target lesions and new measurable lesions).

New lesions are considered measurable at the time of initial progression if the longest diameter is at least 10 mm (except for pathological lymph nodes, which must have a short axis of at least 15 mm). Any new lesion considered non-measurable at the time of initial progression may become measurable and therefore included in the tumor burden measurement if the longest diameter increases to at least 10 mm (except for pathological lymph nodes, which must have an increase in short axis to at least 15 mm).

For statistical analyses that include the investigator-assessed progression date, subjects who continue treatment beyond initial investigator-assessed, RECIST 1.1-defined progression will be considered to have investigator-assessed progressive disease at the time of the initial progression event. Subjects who have tumor shrinkage following RECIST 1.1-defined progression will also be descriptively summarized separately since these immune responses may be used in decision rules for selecting Dose Expansion Phase (Stage 2) study design.

#### **4.5.6 Antiemetic Premedications**

Antiemetic medications should not be routinely administered prior to dosing of drugs. See [Section 4.5.4](#) for subsequent premedication recommendations following ulocuplumab- or nivolumab-related infusion reaction.

#### **4.6 Blinding/Unblinding**

Not applicable.

#### **4.7 Treatment Compliance**

The investigator or designated study personnel will maintain a drug accountability log of all study drug(s); received, dispensed, destroyed and the amount returned to the Sponsor or supply depot. The investigator and study personnel will ensure that each subject receives the calculated dose of the study drug, dependent on either fixed dosing (ulocuplumab) or body weight (nivolumab).

Drug supplies will be inventoried and accounted for throughout the study. The drug accountability log will be reviewed by the study monitor during site visits and at the completion of the study.

#### **4.8 Destruction of Study Drug**

For this study, study drugs (those supplied by BMS or sourced by the investigator) such as partially used study drug containers, vials and syringes may be destroyed on site.

Any unused study drugs can only be destroyed after being inspected and reconciled by the responsible Study Monitor unless study drug containers must be immediately destroyed as required for safety, or to meet local regulations (eg, cytotoxics or biologics).

On-site destruction is allowed provided the following minimal standards are met:

- On-site disposal practices must not expose humans to risks from the drug.
- On-site disposal practices and procedures are in agreement with applicable laws and regulations, including any special requirements for controlled or hazardous substances.
- Written procedures for on-site disposal are available and followed. The procedures must be filed with the site's SOPs and a copy provided to BMS upon request.
- Records are maintained that allow for traceability of each container, including the date disposed of, quantity disposed, and identification of the person disposing the containers. The method of disposal, ie, incinerator, licensed sanitary landfill, or licensed waste disposal vendor must be documented.
- Accountability and disposal records are complete, up-to-date, and available for the Monitor to review throughout the clinical trial period.

If conditions for destruction cannot be met the responsible Study Monitor will make arrangements for return of study drug.

It is the investigator's responsibility to arrange for disposal of all empty containers, provided that procedures for proper disposal have been established according to applicable federal, state, local, and institutional guidelines and procedures, and provided that appropriate records of disposal are kept.

#### **4.9 Return of Study Drug**

If study drug will not be destroyed upon completion or termination of the study, all unused and/or partially used study drug that was supplied by BMS must be returned to BMS. The return of study drug will be arranged by the responsible Study Monitor.

It is the investigator's responsibility to arrange for disposal of all empty containers, provided that procedures for proper disposal have been established according to applicable federal, state, local, and institutional guidelines and procedures, and provided that appropriate records of disposal are kept.

Arrangements for the return of study drug will be made by the responsible Study Monitor.

#### **4.10 Retained Samples for Bioavailability / Bioequivalence**

Not applicable.

## 5 STUDY ASSESSMENTS AND PROCEDURES

### 5.1 Flow Chart/Time and Events Schedule

**Table 5.1-1: Screening Procedural Outline (CA212115)**

Procedure	Screening Visit a	Notes
Call IVRS	X	To obtain subject number
Eligibility Assessments		
Informed Consent	X	
Inclusion/Exclusion Criteria	X	All inclusion/exclusion criteria should be assessed at screening and confirmed prior to first dose.
Medical History	X	
Screening/Baseline Tumor Assessment	X	MRI brain, CT chest, CT/MRI abdomen, pelvis and all other known sites of disease within 28 days prior to first dose. Baseline MRI is required to rule out active brain metastasis (SCLC only).
Safety Assessments		
Physical Examination	X	Within 14 days prior to first dose
Vital Signs and oxygen saturation	X	Including BP, HR, respiratory rate, temperature and oxygen saturation by pulse oximetry (at rest). Obtain vital signs at the screening visit and within 72 hours prior to first dose.
Physical Measurements (including performance status)	X	Height, Weight and ECOG status. Within 14 days prior to first dose
ECG (12-lead)	X	Within 14 days prior to first dose
Chest X-ray	X	Within 14 days prior to first dose
Assessment of Signs and Symptoms	X	Within 14 days prior to first dose
Concomitant Medication Collection	X	Within 14 days prior to first dose

**Table 5.1-1: Screening Procedural Outline (CA212115)**

Procedure	Screening Visit a	Notes
Laboratory Tests	X	CBC w/differential, Chemistry panel including: total protein, LDH, AST, ALT, ALP, total bilirubin, BUN or serum urea level, uric acid, creatinine, albumin, Ca, Mg, Na, P, K, Cl, glucose, amylase, lipase, TSH, Free T4, Free T3, hepatitis B surface antigen (HBV sAg), and hepatitis C antibody (HCV Ab) or Hepatitis C RNA (HCV RNA), within 14 days prior to first dose. Screening labs done within 72 hours prior to first dose can also be used for on treatment lab purposes at Day 1 dosing.
Pregnancy Test (WOCBP only)	X	Serum or urine within 24 hours of first dose
FSH	X	If needed to document post-menopausal status as defined in Section 3.3.3 .
Tumor Tissue Samples	X	Sufficient tumor tissue obtained in the metastatic setting or from an unresectable site (block or minimum of 15 slides, obtained from fresh core biopsy, punch biopsy, excisional biopsy or surgical specimen). Archival sample within 6 months of screening is permitted.

a Within 28 days of treatment

**Table 5.1-2: On-Study Assessments for Dose Evaluation Phase (Stage 1): Ulocuplumab Weekly Dosing (CA212115)**

Procedure	Ulocuplumab administered every week Nivolumab administered every 2 weeks		Notes
	Week 1, 3, 5, 7, 9, etc Ulocuplumab + Nivolumab dosing visits	Week 2, 4, 6, 8, 10, etc Ulocuplumab dosing visits	
Safety Assessments			
Targeted Physical Examination	X	X	Within 72 hours prior to dosing.
Vital Signs and Oxygen Saturation	X	X	Including BP, HR, respiratory rate, temperature and oxygen saturation by pulse oximetry. Pulse oximetry at rest within 72 hours prior to dosing.
Weight	X		Nivolumab dosing calculations should be based on body weight. If the subject's weight on the day of dosing differs by > 10% from the weight used to calculate the dose, the dose must be recalculated. All doses should be rounded to the nearest milligram.
ECOG Status	X		
ECG (12-lead)	See Notes		Every 6 weeks from first dose for the first 12 weeks, then every 12 weeks ( $\pm$ 1 wk)
Adverse Events Assessment	Continuous		
Review of Concomitant Medications	X	X	
Chest X-Ray		X	Week 2 only (monitor for pulmonary toxicity)
Laboratory Tests	X	X	On-study local laboratory assessments should be done within 72 hours prior to each dose: total protein, CBC w/differential, ALT, AST, total bilirubin, direct bilirubin (reflex testing when total bilirubin is elevated), alkaline phosphatase, BUN or serum urea level, uric acid, creatinine, albumin, Ca, Mg, Na, K, P, Cl, LDH, glucose, amylase, lipase, TSH (Free T4 and Free T3 reflex testing if TSH result abnormal).

**Table 5.1-2: On-Study Assessments for Dose Evaluation Phase (Stage 1): Ulocuplumab Weekly Dosing (CA212115)**

Procedure	Ulocuplumab administered every week Nivolumab administered every 2 weeks		Notes
	Week 1, 3, 5, 7, 9, etc Ulocuplumab + Nivolumab dosing visits	Week 2, 4, 6, 8, 10, etc Ulocuplumab dosing visits	
CRP	See Notes		Day 1, then every 6 weeks from first dose for the first 12 weeks, then every 12 weeks ( $\pm 1$ wk)
CA19.9 tumor marker	See Notes		PAC subjects only. Day 1, then every 6 weeks from first dose for the first 12 weeks, then every 12 weeks ( $\pm 1$ wk)
Immunogenicity blood sample	See Notes		Samples will be collected at time points per Section 5.5
Pregnancy Test ( WOCBP only )	See Notes		Serum or urine within 24 hours prior to first dose and then every 4 weeks.
Pharmacokinetic Assessments			
PK Samples	See Notes		Samples will be collected at time points per Section 5.5
Biomarker Testing			
[REDACTED]	[REDACTED]		
[REDACTED]	[REDACTED]		

**Table 5.1-2: On-Study Assessments for Dose Evaluation Phase (Stage 1): Ulocuplumab Weekly Dosing (CA212115)**

Procedure	Ulocuplumab administered every week Nivolumab administered every 2 weeks		Notes
	Week 1, 3, 5, 7, 9, etc Ulocuplumab + Nivolumab dosing visits	Week 2, 4, 6, 8, 10, etc Ulocuplumab dosing visits	
Efficacy Assessment			
Tumor Assessment			
 
• Every 6 weeks (<math>\pm</math> 1 wk) from first dose for the first 24 weeks, then every 12 wks (<math>\pm</math> 1 wk) until disease progression or treatment is discontinued (whichever occurs later).
 
• CT chest, CT/MRI abdomen, pelvis and all known sites of disease. Use same imaging method as was used at screening/baseline.
 
• Subjects with a history of brain metastasis should have surveillance MRI approximately every 12 weeks, or sooner if clinically indicated
 

Outcomes Research Assessment			
EQ-5D	See notes		Assessments should be collected on day 1 and at the same time as tumor assessments. Questionnaires should be completed prior to study drug administration and before any clinical activities.
Clinical Drug Supplies			
IVRS call for vial assignment and randomization	X	X	Randomization call will be implemented after the DLT period, if applicable
Administer Ulocuplumab treatment	X	X	Ulocuplumab will be administered first on days where both therapies are given. See section 4.5 .
Administer Nivolumab treatment	X		See section 4.5

**Table 5.1-3: On-Study Assessments for Dose Evaluation Phase (Stage 1): Ulocuplumab Dosing Every 2 Weeks (CA212115)**

Procedure	Ulocuplumab administered every 2 weeks Nivolumab administered every 2 weeks	Notes
	Week 1, 3, 5, 7, 9, etc Ulocuplumab + Nivolumab dosing visits	
Safety Assessments		
Targeted Physical Examination	X	Within 72 hours prior to dosing.
Vital Signs and Oxygen Saturation	X	Including BP, HR, respiratory rate, temperature and oxygen saturation by pulse oximetry. Pulse oximetry at rest within 72 hours prior to dosing.
Weight	X	Nivolumab dosing calculations should be based on body weight. If the subject's weight on the day of dosing differs by > 10% from the weight used to calculate the dose, the dose must be recalculated. All doses should be rounded to the nearest milligram.
ECOG Status	X	
ECG	See Notes	Every 6 weeks from first dose for the first 12 weeks, then every 12 weeks ( $\pm$ 1 wk)
Adverse Events Assessment	X	
Review of Concomitant Medications	X	
Laboratory Tests	X	On-study local laboratory assessments should be done within 72 hours prior to each dose: total protein, CBC w/differential, ALT, AST, total bilirubin, direct bilirubin (reflex testing when total bilirubin is elevated), alkaline phosphatase, BUN or serum urea level, uric acid, creatinine, albumin, Ca, Mg, Na, K, P, Cl, LDH, glucose, amylase, lipase, TSH (Free T4 and Free T3 reflex testing if TSH result abnormal).

**Table 5.1-3: On-Study Assessments for Dose Evaluation Phase (Stage 1): Ulocuplumab Dosing Every 2 Weeks (CA212115)**

Procedure	Ulocuplumab administered every 2 weeks Nivolumab administered every 2 weeks	Notes
	Week 1, 3, 5, 7, 9, etc Ulocuplumab + Nivolumab dosing visits	
CRP	See Notes	Day 1, then every 6 weeks from first dose for the first 12 weeks, then every 12 weeks ( $\pm 1$ wk)
CA19.9 tumor marker	See Notes	PAC subjects only. Day 1, then every 6 weeks from first dose for the first 12 weeks, then every 12 weeks ( $\pm 1$ wk)
Immunogenicity blood sample	See Notes	Samples will be collected at time points per Section 5.5
Pregnancy Test ( WOCBP only )	See Notes	Serum or urine within 24 hours prior to first dose and then every 4 weeks.
Pharmacokinetic Assessments		
PK Samples	See Notes	Samples will be collected at time points per Section 5.5
Biomarker Testing		
[REDACTED]	[REDACTED]	
[REDACTED]	[REDACTED]	

**Table 5.1-3: On-Study Assessments for Dose Evaluation Phase (Stage 1): Ulocuplumab Dosing Every 2 Weeks (CA212115)**

Procedure	Ulocuplumab administered every 2 weeks Nivolumab administered every 2 weeks	Notes
	Week 1, 3, 5, 7, 9, etc Ulocuplumab + Nivolumab dosing visits	
Efficacy Assessment		
Tumor Assessment		
 
• Every 6 weeks (<math>\pm</math> 1 wk) from first dose for the first 24 weeks, then every 12 wks (<math>\pm</math> 1 wk) until disease progression or treatment is discontinued (whichever occurs later).
 
• CT chest, CT/MRI abdomen, pelvis and all known sites of disease. Use same imaging method as was used at screening/baseline.
 
• Subjects with a history of brain metastasis should have surveillance MRI approximately every 12 weeks, or sooner if clinically indicated
 

Outcomes Research Assessments		
EQ-5D	See notes	Assessments should be collected on day 1 and at the same time as tumor assessments. Questionnaires should be completed prior to study drug administration and before any clinical activities.
Clinical Drug Supplies		
IVRS call for vial assignment and randomization	X	Randomization call will be implemented after the DLT period, if applicable
Administer Ulocuplumab treatment	X	Ulocuplumab will be administered first on days where both therapies are given. See section 4.5
Administer Nivolumab treatment	X	See section 4.5

**Table 5.1-4: On-Study Assessments for Dose Expansion Phase (Stage 2) (CA212115)**

Procedure	Ulocuplumab administered weekly or every 2 weeks Nivolumab administered every 2 weeks a		Notes
	Week 1, 3, 5, 7, 9, etc ulocuplumab + nivolumab dosing visits	Week 2, 4, 6, 8, 10, etc ulocuplumab dosing visits b	
Safety Assessments			
Targeted Physical Examination	X	X	Within 72 hours prior to dosing
Vital Signs and Oxygen Saturation	X	X	Including BP, HR, respiratory rate, temperature and oxygen saturation by pulse oximetry. Pulse oximetry at rest within 72 hours prior to dosing.
Weight	X		The nivolumab dosing calculations should be based on the body weight. If the subject's weight on the day of dosing differs by > 10% from the weight used to calculate the dose, the dose must be recalculated.
ECOG Status	X		
ECG (12-lead)	See notes		Every 6 weeks from first dose for the first 12 weeks, then every 12 weeks ( $\pm$ 1 wk)
Adverse Events Assessment	Continuous		
Review of Concomitant Medications	X	X	
Laboratory Tests	X	X	Local laboratory assessments should be done within 72 hours prior to each dose through Week 24 and every alternate dose thereafter and include total protein, CBC w/differential, ALT, AST, total bilirubin, direct bilirubin (reflex testing when total bilirubin is elevated), alkaline phosphatase, BUN or serum urea level, uric acid, creatinine, albumin, Ca, Mg, Na, K, P, Cl, LDH, glucose, amylase, lipase, TSH (Free T4 and Free T3 reflex test if TSH result abnormal).

**Table 5.1-4: On-Study Assessments for Dose Expansion Phase (Stage 2) (CA212115)**

Procedure	Ulocuplumab administered weekly or every 2 weeks Nivolumab administered every 2 weeks a		Notes
	Week 1, 3, 5, 7, 9, etc ulocuplumab + nivolumab dosing visits	Week 2, 4, 6, 8, 10, etc ulocuplumab dosing visits b	
Efficacy Assessment			
Tumor Assessment	See Notes		Every 6 weeks ( $\pm$ 1 wk) from first dose for the first 24 weeks, then every 12 wks ( $\pm$ 1 wk) until disease progression or treatment is discontinued (whichever occurs later). CT chest, CT/MRI abdomen, pelvis and all known sites of disease. Use same imaging method as was used at screening/baseline. Subjects with a history of brain metastasis should have surveillance MRI approximately every 12 weeks, or sooner if clinically indicated
Clinical Drug Supplies			
IVRS call for vial assignment and randomization	X	X	Randomization call will be implemented if a phase 2 randomized study design is initiated
Administer Ulocuplumab treatment (See section 4.5)	X	X	Ulocuplumab will be administered first on days where both therapies are given. For 1600mg every 2 week dosing, ulocuplumab doses will be given Week 1, 3, 5, etc. b
Administer Nivolumab treatment (See section 4.5)	X		If a randomized phase 2 design is initiated for SCLC, the comparator will be nivolumab monotherapy every 2 weeks
Investigator choice chemotherapy treatment	X	X	If a randomized phase 2 design is initiated for PAC, the comparator will be investigator choice chemotherapy

a If a randomized phase 2 design is initiated for SCLC, the comparator will be nivolumab monotherapy following the every 2 week visit schedule (eg, week 1, 3, 5, 7, etc.). If a randomized phase 2 design is initiated for PAC, the comparator will be investigator choice chemotherapy following the weekly visit assessments, as applicable.

b For ulocuplumab every 2 week dosing, ulocuplumab doses will be given Week 1, 3, 5, etc. Visits at Week 2, 4, 6, etc. will not be required.

Table 5.1-5: Follow-up Assessments (CA212115) - All Subjects			
Procedure	Follow Up,a Visits 1 and 2	Survival,b Follow up Visits	Notes
Safety Assessments			
Targeted Physical Examination	X		
Adverse Event Assessments	X	X	AEs during the survival follow up visits considered study drug-related should be followed until resolution, stabilization, or returned to baseline.
Laboratory Tests	X		CBC w/differential, total protein, ALT, AST, total bilirubin, direct bilirubin (reflex testing when total bilirubin is elevated), alkaline phosphatase, BUN or serum urea level, uric acid, creatinine, albumin, Ca, Mg, Na, K, P, Cl, LDH, glucose, amylase, lipase, TSH (Free T4 and Free T3 reflex testing if TSH result abnormal).
Pregnancy Test (WOCBP Only)	X		Serum or urine
Review of Concomitant Medications	X		
PK Samples	X		See section 5.5
Immunogenicity blood sample	X		See section 5.5
Survival Status			
Subject Status	X	X	Every 3 months, may be accomplished by visit, phone contact or email, to assess subsequent anti-cancer therapy
Efficacy Assessments			
Tumor Assessment		See Notes	
Only for subjects without progression on study therapy and even if they receive subsequent treatment.
 
Every 6 weeks (<math>\pm</math> 1 wk) from first dose for the first 24 weeks, then every 12 wks (<math>\pm</math> 1 wk) until disease progression or treatment is discontinued (whichever occurs later).
 
CT chest, CT/MRI abdomen, pelvis and all known sites of disease. Use same imaging method as was used at screening/baseline.
 
Subjects with a history of brain metastasis should have surveillance MRI approximately every 12 weeks, or sooner if clinically indicated

Table 5.1-5: Follow-up Assessments (CA212115) - All Subjects			
Procedure	Follow Up,a Visits 1 and 2	Survival,b Follow up Visits	Notes
Outcomes Research Assessments			
EQ-5D	X	X	The EQ-5D can be done via a phone contact when a clinic visit is not feasible (ie, follow up scans are being done at another facility or department) in order to not miss the assessment.
Cancer-specific questionnaire* LCSS (SCLC) EORTC-QLQ-C30 (PAC)	X	X	*Only for Stage 2 Randomized study subjects

a Follow-up visit 1 (FU1) = 35 days ( $\pm$  7 days) from the last dose or coincide with the date of discontinuation ( $\pm$  7 days) if date of discontinuation is greater than 42 days after last dose, Follow-up visit 2 (FU2) = 80 days ( $\pm$  7 days) from follow-up visit 1

b Survival visits = every 3 months from FU2. Regardless of any subsequent treatment, all subjects will remain on study follow-up for disease progression and survival assessment.

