**Study Drug:**

Study Drug for CA212115		
Medication	Potency	IP/Non-IP
Ulocuplumab (BMS-936564)	100 mg (10 mg/mL)	IP
Nivolumab (BMS-936558)	100 mg (10 mg/mL)	IP

**Study Assessments:** Radiographic tumor assessments will be performed at baseline, at 6 weeks from first dose and continue every 6 weeks for the first 24 weeks and every 12 weeks thereafter until disease progression or treatment discontinuation.

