## 8.3 Endpoints

### 8.3.1 Primary Endpoint(s)

The incidence of DLTs is the primary safety endpoint during the DLT evaluation phase.

In terms of efficacy, the primary endpoint for SCLC is investigator assessed ORR for the Dose Evaluation Phase and the single arm Dose Expansion Phase. If the randomized Phase 2 study in SCLC subjects is triggered, an IRRC will perform blinded independent review of the imaging per RECIST 1.1 criteria for the assessment of ORR. The ORR is defined as the number of subjects with a best overall response (BOR) of complete response (CR) or partial response (PR) divided by the number of treated subjects (the number of randomized subjects for the randomized Phase 2 study with comparative arm). The BOR is defined as the best response designation, as determined by the investigator, recorded between the first dosing date (randomization date for the randomized Phase 2 study with comparative arm) and the date of objectively documented progression per RECIST 1.1 or the date of subsequent anti-cancer therapy, whichever occurs first. CR or PR determinations included in the BOR assessment must be confirmed by a second scan no less than 4 weeks after the criteria for response are first met. For subjects without documented progression or subsequent therapy, all available response designations will contribute to the BOR assessment. For subjects who continue treatment beyond

progression, the BOR should be determined based on response designations recorded up to the time of the initial RECIST 1.1-defined progression.

For PAC, the primary endpoint is investigator assessed ORR for the Dose Evaluation Phase and the single arm Dose Expansion Phase. Overall survival (OS) is the primary endpoint for the randomized two-arm Phase 2 study. The ORR is defined as above and OS is defined as the time between the randomization date and the date of death due to any cause. A subject who has not died will be censored at the last known alive date.

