### **8.3.2 Secondary Endpoint(s)**

Safety and tolerability will be analyzed through the incidence of DLTs, adverse events, serious adverse events, and specific laboratory abnormalities (worst grade). Toxicities will be graded using the NCI CTCAE version 4.0.

PFS is defined as the time from first dosing date (randomization date for the randomized Phase 2 study with comparative arm) to the date of the first documented tumor progression, as determined by the investigator (per RECIST 1.1), or death due to any cause, whichever occurs first. Subjects who die without a reported prior progression will be considered to have progressed on the date of their death. Subjects who did not progress or die will be censored on the date of their last evaluable tumor assessment. Subjects who did not have any on-study tumor assessments and did not die will be censored on the date of their first dosing date (randomization date for the randomized Phase 2 study with comparative arm). Subjects who started anti-cancer therapy without a prior reported progression will be censored on the date of their last evaluable tumor assessment prior to the initiation of subsequent anti-cancer therapy.

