### **8.4.2 Efficacy Analyses**

For the Dose Evaluation Phase, efficacy analyses will be summarized using the All Dose Evaluation Randomized Treated Subjects by randomized cohort (primary population). Additionally, analyses including all efficacy data collected during that Phase using the All Treated Subjects population will be provided by regimen. Analyses will be presented as-treated.

If the form of the Expansion Phase is a Simon 2-stage like design, efficacy analyses will be summarized for the regimen recommended for the Dose Expansion Phase, pooling data from the related randomized cohort from the All Dose Evaluation Randomized Treated Subjects during Stage 1 with the Stage 2 data (primary population). Additionally, analyses using the All Treated Subjects and including all efficacy data collected for that regimen during the Dose Evaluation and the Dose Expansion Phases will be provided. Analyses will be presented as-treated.

If a randomized Phase 2 study with comparative arm is initiated, efficacy analyses will be presented separately by treatment arm using the All Expansion Phase Randomized Subjects. Analyses will be presented as-randomized.

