#### **8.4.2.2 Secondary Endpoint Methods**

PFS as a secondary endpoint will be descriptively summarized as for OS above. PFS rates at 3, 6, 9, 12, and 18 months will be estimated as well as associated two-sided 95% CIs considering a log-log transformation.

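### In the randomised Phase 2, scans are scheduled from first dose but PFS is counted from randomisation, so an arm difference in time to first dose can shift observed PFS with no true effect

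*Protocol*

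**What the plan says.** **Scan calendar.** Table 5.1-4 covers Stage 2, including both randomised options and their comparators. It sets tumour assessments every 6 weeks (±1 week) "from first dose for the first 24 weeks, then every 12 wks". The Synopsis has them "at 6 weeks from first dose and continue every 6 weeks for the first 24 weeks and every 12 weeks thereafter". Table 5.1-5 and Section 5.4 also count from first dose. Section 5.3.1.1 repeats the intervals without naming an origin. None of these makes an exception for the randomised design.

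**Endpoint clock.** Section 8.3.2 changes the origin for that design only: "PFS is defined as the time from first dosing date (randomization date for the randomized Phase 2 study with comparative arm"). Section 8.3.1 does the same for best overall response, "recorded between the first dosing date (randomization date for the randomized Phase 2 study with comparative arm"). Under Section 8.4.2, "efficacy analyses will be presented separately by treatment arm using the All Expansion Phase Randomized Subjects", as randomised.

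**Status of PFS.** PFS is secondary in both randomised studies (Section 3.1.3). Section 8.4.2.2 says "PFS as a secondary endpoint will be descriptively summarized as for OS above" and adds that "PFS rates at 3, 6, 9, 12, and 18 months will be estimated as well as associated two-sided 95% CIs".

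**Interval between the dates.** No maximum is given. Section 6.1.1 foresees subjects who are randomised and never treated. The SAP (Section 2) leaves out the analyses of the randomised part for now, so it does not settle the point.

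**The concern.** Progression is seen only at scans, which are 6 and later 12 weeks apart. If one arm starts treatment later after randomisation than the other, its whole scan grid sits later on the PFS clock. The two arms are then inspected at different times since randomisation, and observed PFS can differ between them even when true PFS is identical. The 3-month rate is the most exposed planned summary, because the Week 12 scan (day 84, window days 77 to 91) falls just before the 3-month mark (day 91.3).

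An arm difference in start date is plausible mainly in PAC. There the trial is open label and compares two investigational antibodies with investigator's-choice chemotherapy, which Section 4.2 classes as non-investigational product.

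A subject who is randomised but never dosed has no scan calendar at all. If alive and without on-study scans, that subject is censored at randomisation under Section 8.3.2.

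**Working it through.** **The plan's own figures.** The documents give no figure for PFS or for the randomisation-to-first-dose gap. The nearest checkable figure is the PAC event count (Section 8.1.2: hazard ratio 0.75, one-sided alpha 0.10, 80% power): 4 × (1.2816 + 0.8416)² / (ln 0.75)² = 217.9, so 218 deaths, as stated. The 125 subjects per arm used below come from the same section.

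**Inputs.** From the plan: scans at weeks 6, 12, 18, 24 and then every 12 weeks from first dose, ±1 week; 125 per arm. Assumed: the same exponential true PFS in both arms with median 8 weeks (λ = ln 2 / 56 = 0.01238 per day), scan dates uniform over the window, and first dose 3 days after randomisation in one arm and 10 days in the other.

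**Formula.** Without deaths, a subject counts as progression-free at 3 months if there was no progression by the last scan on or before day 91.3. With p the chance that the Week 12 scan falls by day 91.3:

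observed rate = p × mean of exp(−λ × Week 12 scan day, given it is by day 91.3) + (1 − p) × mean of exp(−λ × Week 6 scan day)

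- Gap 3 days: the Week 12 scan falls on days 80 to 94, so p = (91.3 − 80)/14 = 0.808. Rate = 0.808 × 0.347 + 0.192 × 0.574 = 39.0%.
- Gap 10 days: it falls on days 87 to 101, so p = 0.308. Rate = 0.308 × 0.332 + 0.692 × 0.526 = 46.6%.
- Difference: 7.6 points.

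**Noise.** Standard error of the difference = √[(0.390 × 0.610 + 0.466 × 0.534)/125] = 6.2 points. The artefact is about 1.2 standard errors.

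**With deaths.** Deaths are PFS events whatever the scan date. If 30% of the hazard is death, progression uses 0.7λ and the rate is multiplied by exp(−0.3λ × 91.3) = 0.712. The rates become 36.7% and 41.6%, a difference of 4.9 points.

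**Other landmark.** At 6 months (day 182.6), without deaths, the same gaps give 12.1% and 12.5%.

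**Direction.** Take a 2-month median, 20% of the hazard from death and scans exactly on schedule:

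| Gap | Last scan by day 91.3 | 3-month rate |
|---|---|---|
| 0 days | day 84 | 37.8% |
| 7 days | day 91 | 35.5% |
| 14 days | day 56 | 48.8% |

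The rate first falls and then jumps, so a later start can move it either way.

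**Hazard ratio, and the effect of re-anchoring.** A simulation used no true difference, median PFS of 1.5 to 4 months, 20% of the hazard from death, and a delay in one arm only. For a 7-day delay with the ±1 week window it gave hazard ratios of 0.89 to 0.94 in favour of the delayed arm. Mean observed PFS moved by only about 1 to 2 days. With scans anchored to randomisation in both arms, delays of 7 and 14 days gave 0.99 to 1.01. The plan specifies no hazard ratio or test for PFS, so these values only show the mechanism and its removal.

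**The case against.** **The trigger is not in the documents.** Bias needs a gap that differs by arm, and no gap is stated. Table 5.1-4 puts the randomisation and vial-assignment call in the dosing-visit columns, and Section 4.4 runs treatment and vial assignment through the same system. Both suggest a short gap. This stands, and it limits the likely size. But nothing caps the interval, and Section 6.1.1 shows the two dates are not taken to coincide.

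**The consequence is limited.** PFS is descriptive with no planned test. The randomised part starts only after at least 9 of 19 (SCLC) or 6 of 21 (PAC) responders, and its analyses may still be added to the SAP. This also stands.

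**Stronger readings that a reader might infer do not hold.**
- *Every progression is detected later in the slower arm.* A shifted grid also catches some progressions one scan earlier, and landmark rates can fall as well as rise.
- *The primary endpoints are biased.* OS does not depend on scans. The origin for best response also moves to randomisation, but no scan is scheduled between randomisation and first dose, so confirmed ORR should change little.
- *SCLC is equally exposed.* There "the comparator will be nivolumab monotherapy every 2 weeks", and the experimental arm also receives nivolumab. The documents offer no reason for the start dates to differ.
- *The whole gap between 46.6% and the true 32% is due to the offset.* Scanning at intervals alone gives 35.4% with no gap, and re-anchoring would not remove that part.
- *The artefact far exceeds chance variation.* That impression comes from comparing a between-arm difference with the single-arm standard error of about 4.4 points.

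**Conclusion.** The mismatch holds: in the randomised Phase 2 the scan calendar and the PFS clock have different origins, and nothing in either document reconciles them or bounds the interval between them. If the interval differs by arm, observed PFS can differ with no true effect.

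The size is moderate and conditional: about 5 to 7.5 points on the 3-month rate, depending on the share of deaths, and almost nothing at 6 months. It rests on assumed gaps of 3 and 10 days, an 8-week median and uniform scan windows. Equal gaps give no bias. The point concerns one descriptive secondary endpoint, chiefly in PAC, and the missing scan calendar for subjects never dosed. It is worth correcting because the change is cheap before the randomised part opens, and scan timing cannot be repaired once the data are collected.

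**What to change.** For the randomised Phase 2 only, schedule tumour assessments in both arms from the date of randomisation: every 6 weeks ±1 week to Week 24, then every 12 weeks. State that this applies whatever the first-dose date and includes subjects never dosed. Make the same change in the Synopsis, Table 5.1-4, Table 5.1-5 and Sections 5.3.1.1 and 5.4, since editing one place would leave the others in conflict. Keep the first-dose anchor for the single-arm phases, where PFS also starts at first dose. When the randomised analyses are added to the SAP, include a summary by arm of the interval from randomisation to first dose.

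Cost: protocol wording in those places. Some scans will fall a few days off the dosing cycle, and a late-starting subject will have slightly less drug exposure before the first scan. The 218 deaths, 125 per arm in PAC and 50 per arm in SCLC do not change.
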